3.3. Treatment Adherence

Treatment adherence based on drug accountability will be summarized by means of descriptive statistics and frequency tabulations. Cumulative treatment adherence will be calculated from baseline to the switch, and again from the switch to Week 96. Cumulative treatment adherence will be determined (derivation i).

The following parameters are derived:

Amount to be taken through switch/Week 96 = (number of days since start of treatment/switch × number of tablets to be taken per day).

Number of days since start of start of treatment/switch is based on (whichever comes sooner):

- last study medication intake (if available) or, in case subject discontinued and last study medication intake is missing, the last visit date prior to withdrawal will be used.
- Switch/Week 96 visit date,

In addition (derivation ii), the cumulative treatment adherence up to time point where not more than one bottle is missing, or if available, up to switch/Week 96, whichever comes sooner, will be calculated.

Actual amount taken = (number of tablets dispensed – number of tablets returned), summed over time points up to the time point of interest.

Level of adherence = (actual amount taken / amount to be taken) \times 100%

Treatment adherence is defined as:

- adherent: the level of adherence is >95%,
- non-adherent: the level of adherence is \leq 95%.

Additionally, following categories of level of adherence will be defined:

- >95%
- [80%; 95%]
- [65%; 80%]
- [50%; 65%]
- < 50%

Interruptions (for AEs) are not to be taken into account for the calculation of adherence, i.e. they will not be subtracted from the amount to be taken.

Within treatment group comparison using McNemar's Exact test comparing adherence (i.e., adherent versus non-adherent) before and after the switch will be calculated. The statistical test will be interpreted at the 5% two-sided significance level.

3.4. Extent of Exposure

Descriptive statistics will be tabulated for the duration of treatment of both treatment groups, in weeks, during the respective active treatment phases, as of reference up to the Week 96 visit or in case of early discontinuation, last study medication intake. In addition, subject-years of exposure will be shown, derived as mean of treatment duration (in weeks) x N) x 7 / 365.25. Tabulation of the distribution of exposure per 4 week intervals will be presented. Additionally, the number (with percentages) of subjects who switched by analysis time point will be provided along with the subject-years of exposure to D/C/F/TAF per analysis time point.

Treatment duration (in weeks) is derived as follows:

(End of phase - reference + 1) / 7

Treatment interruptions will not be taken into account for the above definition.

3.5. Protocol Deviations

All major protocol deviations will be tabulated and listed by treatment arm and overall. The proportion of subjects with one or more major protocol deviation that led to exclusion from the per protocol analysis set (see Attachment 1) will also be tabulated.

3.6. Concomitant Medications

Concomitant medications are defined as any therapy used on or after the same day as the first dose of study agent, including those that started before and continue on after the first dose of study agent.

Combination drugs are split up into their respective compounds.

Concomitant therapies will be grouped as follows, using a list of dictionary derived terms provided as metadata. These groups will be tabulated (n, %) per treatment group and analysis phase:

- lipid lowering drugs
- antidiabetic drugs
- antihypertensive drugs
- drugs for cardiovascular disease
- antiosteoporotic drugs

4. EFFICACY

4.1. Analysis Specifications

4.1.1. Level of Significance

No formal statistical tests will be performed. All analyses will be descriptive.

4.1.2. Data Handling Rules

Plasma viral load levels will be measured using the ROCHE COBAS® AmpliPrep/COBAS® Taqman® HIV-1 Test, v2.0, which will be conducted by the central laboratory.

Imputation of left censored HIV-1 RNA values: viral load results recorded as "< 20 HIV-1 RNA copies/mL detected" and "< 20 HIV-1 RNA copies/mL not detected" will be scored at 19.

CD4+ cell count and HIV-1 RNA data collected on treatment (up to the last dose date of study drug) will be used in the analysis.

4.1.3. FDA Snapshot Approach and Time to Loss of Virologic Response Algorithm (TLOVR)

FDA Snapshot approach (applying 20/50/200 copies/mL as threshold): The Snapshot approach will classify subjects into 3 outcome categories: "virologic success", "virologic failure", or "no viral load data in the Week 96 visit window". Several subcategories of the outcome will also be presented in the analysis and are shown below. The categories below are mutually exclusive such that a subject will be included in one (sub)category. If a subject discontinues in the time window but also has an HIV-RNA value in the time window then the viral load value will be used to classify the subject's category.

- Virologic success:
 - Last available HIV RNA <20/50/200 copies/mL in the Week 96 visit window (Week 90-102)
- Virologic failure:
 - Last available HIV RNA ≥20/50/200 copies/mL in the Week 96 visit window (Week 90-102)
 - Virologic failure leading to discontinuation
 - o Discontinued due to other reason (i.e., other than AE/death or virologic failure) and last available HIV RNA ≥20/50/200 copies/mL
- No viral load data in the Week 96 visit window:
 - Discontinued due to AE/death (subjects will be classified in this category if discontinued prior to Week 96 window regardless of HIV RNA level)
 - O Discontinued due to other reason (i.e., other than AE/death or virologic failure) and the last available HIV RNA <20/50/200 copies/mL (or missing)
 - o Missing data during the Week 96 visit window but on study

'Virologic failure' as reason for discontinuing the trial was inadvertently not included in the Study Termination eCRF page. Therefore, whether a subject would be classified into the subcategory 'Virologic failure leading to discontinuation' will be determined by a medical assessment of the comment fields and other specification reasons for discontinuation to determine if anyone discontinued the trial due to lack of efficacy reasons. A current list of comments and other specification reasons are documented in Attachment 5, and will be used to programmatically identify such subjects. Upon further clinical evaluation additional comments or other specification reasons might need to be added, and these will be documented in the DPS. An identified subject will be classified to the Snapshot categories as follows:

- Data within window: If an identified subject has HIV RNA value within the window, the last HIV RNA value will be used to classify the subject as either at or above the threshold or below the threshold
- No data within window: If an identified subject does not have an HIV RNA value in window, then regardless of the last HIV RNA value the subject will be classified as "Virologic failure leading to discontinuation"

Virologic response will then be categorized as follows: Yes (virologic success), or No (virologic failure and no viral load data in the Week 96 visit window).

The Snapshot approach will also be displayed over time by analysis time point, and will follow the same logic as defined above (please see Section 2.2.2 for visit intervals)

Imputations for missing values

The following imputation method is used to calculate **virologic response** at a given time point:

- observed case: subjects with a missing value are disregarded in the analysis for that time point.
- TLOVR: responders/non-responders are defined according to the FDA Time To Loss Of Virologic Response algorithm; a subject is considered a responder at a given time point if the applicable HIV-RNA criterion is fulfilled at that time point and at the subsequent time point; a subject is considered a confirmed non-responder at a time point in the following situations in order of precedence:
 - o the subject shows a 'rebound' HIV-RNA value (>=threshold copies/mL) at that time point and the subsequent time point;
 - o the subject shows a confirmed rebound at an earlier time point (irrespective of resuppression of viral load)
 - o the subject (permanently) discontinued at that time point or before
 - intermittently missing values are considered as response if the immediately preceding and following visits demonstrated response; in case the subject had not reached the next visit yet, no imputation is performed for the missing time points, unless the subject had discontinued the trial.
 - Remark: in case multiple virologic response observations are available within the same time window, all observations are used to determine TLOVR-imputed response for that time window. In case the subject has not reached the next visit yet, this subject is left out of the analysis for the missing time points.

4.2. Primary Efficacy Endpoint(s)

4.2.1. Definition

The primary efficacy endpoint of this study was the proportion of subjects who have HIV-1 RNA <50 copies/mL at Week 48 as defined by the FDA Snapshot analysis. Thus, the analysis of this endpoint is not described in the Week 96 SAP.

4.2.2. Analysis Methods

Not applicable.

4.3. Major Secondary Efficacy Endpoints

4.3.1. Definition

- The proportion of subjects with HIV-1 RNA <20, <50, and <200 copies/mL at Week 96 as defined by the FDA Snapshot analysis;
- The proportion of subjects with HIV-1 RNA <20, <50, and <200 copies/mL at Week 96 as defined by the time to loss of virologic response (TLOVR) algorithm;
- The change from reference in log₁₀ HIV-1 RNA up to Week 96;
- The change from reference in CD4+ cell count up to Week 96;
- The development of viral resistance through Week 96;

4.3.2. Analysis Methods

4.3.2.1. Antiviral Efficacy

Tabulations (numbers and proportions) per time point will be provided for the Snapshot outcomes (success, failure, no data within window). Tabulations (numbers and proportions) will also be provided for Snapshot outcome at Week 96 based on observed data (i.e., subjects with a missing value are disregarded in the analysis for that time point), and TLOVR through Week 96. The exact 2-sided 95% CIs around in each treatment group will be calculated by the Clopper-Pearson method for Snapshot virologic success and virologic failure, and TLOVR response. Bar charts will be presented for Snapshot outcomes.

Cross-tabulations for protocol defined virologic failure (see Section 4.3.2.3) versus the FDA snapshot algorithm at Week 96 (HIV-1 RNA < 50 copies/mL) will be presented.

4.3.2.2. Immunologic Change

Change from reference is defined as: value at a given time point minus reference value.

Actual and changes from reference values in CD4+ cell count and log₁₀ HIV-1 RNA at each time point will be summarized using descriptive statistics (n, mean (SE), median, min, and max).

The changes from reference in CD4+ cell count (NC=F) and log₁₀ HIV-1 RNA (NC=F) at Week 96 will be constructed using analysis of covariance (ANCOVA), separately for each treatment group, including CD4+ cell count or log₁₀ HIV-1 RNA at reference, respectively, as continuous covariate in the model.

Subjects who discontinue will have their CD4 or log₁₀ HIV-1 RNA values after discontinuation imputed with their reference value, thus resulting in a 0 change (NC=F). Other (intermittent) missing values will be imputed using last observation carried forward (LOCF). Apart from imputed, observed data will also be presented. For cases where no observation is available at the baseline date, the last available screening value will be taken.

A supportive mixed model for repeated measures in change from reference in CD4+ cell count (observed) will also be performed separately for each treatment group. The model will include post-baseline change from reference as a response variable, terms for visit, and the corresponding reference value as a covariate An unstructured covariance matrix will be used to model the correlation among repeated measurements.

Cross-tabulations of Week 96 CD4 cell count versus reference will be provided using the categories: $< 200, 200 \le x < 350, 350 \le x \le 500, >500 \text{ cells/mm}^3$.

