# **Key Inclusion Criteria**

Subjects must be ARV treatment-naïve (never treated with an ARV including post-exposure prophylaxis and pre-exposure prophylaxis); no prior use of any approved or experimental anti-HIV drug for any length of time.

Screening plasma HIV-1 RNA level ≥1,000 copies/mL

CD4+ cell count >50 cells/μL.

Screening HIV-1 genotype report must show full sensitivity to DRV, TDF and FTC.

Screening eGFR $_{\text{creatinine}} \ge 70 \text{ mL/min}$  according to the Cockcroft-Gault formula for creatinine clearance.

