2.6. Reference

For Initial D/C/F/TAF group, reference is the comparative treatment phase baseline as in Week 48 analysis. For the Late Switch group, the references are as follows:

- 1. Comparative treatment phase baseline (for efficacy this reference will be used for periods before and after the switch; for safety this reference will be used for periods before the switch).
- 2. Last value prior to the switch will be used as a reference for periods after the switch for both efficacy and safety; for DXA scan, data up to (and including) 28 days after the switch to open label D/C/F/TAF can be used as reference.

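### The one-arm Week 96 ANCOVA leaves each arm's mean change as it is and only shrinks its standard error, so any SE or interval taken from it overstates precision

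*SAP*

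**What the plan says.** SAP 4.3.2.2 (Immunologic Change) covers change from reference in CD4+ count and log10 HIV-1 RNA, both listed among the major secondary efficacy endpoints in SAP 4.3.1.

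- **Model.** The change "at Week 96 will be constructed using analysis of covariance (ANCOVA), separately for each treatment group". The reference value of the same variable is the only covariate. The section does not say at which reference value the mean is evaluated, and it names no confidence interval for this model.
- **Missing data.** Subjects who discontinue have later values "imputed with their reference value, thus resulting in a 0 change (NC=F"). Intermittent gaps are filled by LOCF, and observed data are shown as well.
- **Raw summary.** Actual values and changes at each time point "will be summarized using descriptive statistics (n, mean (SE), median, min, and max").
- **Assay floor.** Under SAP 4.1.2, results below 20 copies/mL, detected or not, "will be scored at 19".
- **Reference.** The Late Switch arm has two references. One is the original baseline. The other, in SAP 2.6, is: "Last value prior to the switch will be used as a reference for periods after the switch for both efficacy and safety".
- **Status.** SAP 4.1.1: "No formal statistical tests will be performed. All analyses will be descriptive".

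**The concern.** A baseline covariate earns its place in a two-arm model, where it removes chance imbalance and sharpens the contrast. Protocol 11.4.2 uses ANCOVA in that way for the Week 48 difference in CD4+ change, and there it asks for a 95% interval. The Week 96 plan keeps the covariate but drops the contrast.

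In a one-arm model the covariate can only take out variance explained by the reference. That variance is a real part of the uncertainty about the mean change in the population from which the arm was drawn. Change is defined as value minus reference, so the two are correlated by construction. The link is tightest for viral load: a suppressed subject always scores 19 copies/mL, so the change is log10(19) minus the reference, a slope of exactly -1.

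At stake is the precision reported for two major secondary endpoints. The same NC=F mean could appear once with its raw SE and once with a smaller model SE, with no rule saying which to report. In the Late Switch arm the mean change from the pre-switch reference should be near zero, so a falsely tight interval could suggest a shift in viral load after the switch that is not there.

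**Working it through.** **1. The plan's own figure.** The documents give no SE, SD or correlation for this analysis. The only figure to reproduce is the sample size, which supplies n. With 80% response in both arms, a 10% margin, one-sided 0.025 and 90% power: n = (1.960 + 1.282)² × 2 × 0.8 × 0.2 / 0.10² = 337 per arm, against 335 stated. Power at 335 is 89.9%. This agrees with the plan but does not test the point.

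**2. Algebra.** In a one-arm regression of change on reference, the fitted value at the mean reference is the raw mean change. A numerical check gave -2.7773 by both routes. The SEs are:

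- raw: SD(change)/sqrt(n);
- model: residual SD/sqrt(n), which is the raw SE × sqrt(1 - r²), apart from a negligible degrees-of-freedom term.

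Coverage of the population mean by a nominal 95% model interval is about 2Φ(1.96 × sqrt(1 - r²)) - 1.

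**3. r² under NC=F.** Let d be the share discontinued (change 0), and for the rest let b be the slope, V the reference variance, s² the residual variance and g the mean change. Then

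r² = (1-d)² b² V / [(1-d)(b²V + s² + g²) - (1-d)² g²].

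**4. log10 HIV-1 RNA.** From the documents: n = 335; floor log10(19) = 1.279; screening entry criterion "Screening plasma HIV-1 RNA level ≥1,000 copies/mL", that is 3.0 log10. Assumed: reference mean 4.5 and SD 0.7, s = 0.15, b = -1, so g = 1.279 - 4.5 = -3.221 and g² = 10.375.

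At d = 10%: numerator 0.81 × 0.49 = 0.397; denominator 0.9 × (0.49 + 0.0225 + 10.375) - 0.81 × 10.375 = 1.395; r² = 0.284; SE ratio sqrt(0.716) = 0.846; coverage about 90%.

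Simulation (4,000 arms of 335; 95% of those on drug at the floor, the rest above it by an exponential amount with mean 0.5 log10; reference not below 3.0):

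| Discontinued | SE ratio, model/raw | 95% half-width, model → raw | Coverage, model | Coverage, raw |
|---|---|---|---|---|
| 0% | 0.21 | 0.016 → 0.076 | 33% | 95% |
| 5% | 0.74 | 0.078 → 0.105 | 86% | 95% |
| 10% | 0.85 | 0.107 → 0.126 | 91% | 96% |
| 15% | 0.89 | 0.126 → 0.141 | 92% | 95% |
| 20% | 0.92 | 0.141 → 0.153 | 93% | 95% |

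For reference SDs of 0.5 to 0.8 the formula gives ratios of 0.81-0.91 at 10% discontinued and 0.90-0.96 at 20%. The NC=F zeros add residual variance, which is why the shrinkage eases as discontinuation rises.

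**5. Late Switch arm, pre-switch reference.** Same floor and excess distribution, n = 335 assumed.

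- 5% viraemic both before the switch and at Week 96: SE ratio 0.69-0.75 and coverage 81-84% for 0-20% discontinued.
- 5% before and 3% after: coverage 75-78%.
- 8% before and 4% after, 5% discontinued: 74%.

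The raw interval stays near 95% throughout. A larger fall in the viraemic share would lower model coverage further.

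**6. CD4+.** Assumed reference SD 220, residual SD 170 and mean change 220 cells, with 0-20% discontinued:

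| Slope on reference | SE ratio | Coverage |
|---|---|---|
| -0.2 | 0.97-0.98 | 94-95% |
| -0.3 | 0.93-0.96 | 93-94% |
| -0.5 | 0.84-0.90 | 90-92% |

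At slope -0.2 and 15% discontinued the half-width moves only from 18.9 to 19.3 cells.

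**The case against.** The case on the other side is substantial, and most of it limits the point without removing it.

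- **No interval is planned.** A reader might infer that the SAP will publish Week 96 confidence intervals for change that are too narrow. The section does not say so. Where the SAP wants efficacy intervals it names them, as in SAP 4.3.2.1 (Clopper-Pearson). The point therefore concerns any SE or interval taken from the model. It stands because, with the mean unchanged, a different SE is all the model can add.
- **The raw mean and SE are already tabulated, and Week 96 is descriptive.** Both are true. No decision depends on this output and the Week 48 primary analysis is untouched. But a descriptive SE should still describe the mean it accompanies, and two SEs for one mean need a rule.
- **The model SE is valid conditional on the observed reference values.** Correct. The SAP states no such target, however, and an arm's mean change is normally read as applying to the treated population.
- **The unchanged mean assumes evaluation at the arm's own mean reference.** That is the usual default but is not written down. At a reference value common to both arms the fitted means would differ from the raw ones.
- **Viral load is not always the worse case.** At 20% discontinued, RNA with reference SD 0.5 gives a ratio of 0.956, while CD4+ with slope -0.4 gives 0.931. The near-collapse of the RNA interval needs almost no discontinuations.
- **The supportive CD4+ repeated-measures model.** It "will also be performed separately for each treatment group", so a reader might infer the same fault. That does not follow. It uses observed data, and if missingness is related to the reference, the covariate can legitimately move the fitted visit means. No calculation here supports extending the point to it.

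**Conclusion.** The point holds in a limited form. The direction is algebraic: for the population mean change, with evaluation at the arm's mean reference, the model SE is smaller than the raw SE whenever change and reference are correlated.

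The size rests on assumed SDs, slopes, viraemic shares and discontinuation rates, none of which the documents supply. At 10-20% discontinued the log10 RNA interval would be about 4-19% too narrow. The Late Switch pre-switch analysis is hit harder, around a mean change close to zero. The CD4+ effect is negligible at shallow slopes.

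The consequence is misleading error bars on two descriptive secondary outputs. No study conclusion is put in doubt, but the sentence is worth changing because the model as written has nothing else to offer.

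**What to change.** In SAP 4.3.2.2, replace the within-arm ANCOVA sentence with: each arm's mean change from reference at Week 96, for NC=F and observed data, with SE = SD/sqrt(n) and a 95% t-interval. State explicitly that an interval is shown, and for which reference in the Late Switch arm. If a model is wanted, fit one model with arm and reference, and use it for a between-arm contrast only where such a contrast is intended. The repeated-measures sentence need not change on this account.

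The cost is one sentence and simpler programming. Relative to model-based intervals at the arm's mean reference, point estimates do not move and intervals become slightly wider; in the RNA example at 10% discontinued the half-width goes from 0.107 to 0.126 log10.

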4.3.2.3. Resistance Determinations

Subjects who are on study medication and who experience a protocol defined confirmed virologic failure, i.e., virological non-response (NR), virologic rebound (RB), or viremic at final time point, as defined below, will be considered to have VF for the purpose of the resistance analysis.

Virologic Nonresponse:

• HIV-1 RNA <1 log₁₀ reduction from baseline and ≥50 copies/mL at the Week 8 visit, confirmed at the following scheduled or unscheduled visit following Week 8.

Virologic Rebound:

- At any visit, after achieving confirmed (consecutive) HIV-1 RNA <50 copies/mL, a rebound in HIV-1 RNA to ≥50 copies/mL, which is subsequently confirmed at the following scheduled or unscheduled visit;
 or
- At any visit, a >1 log₁₀ increase in HIV-1 RNA from the nadir which is subsequently confirmed at the following scheduled or unscheduled visit.

Virologic at Final Time Point:

 Any subject with on-treatment HIV-1 RNA ≥400 copies/mL at the study endpoint or study discontinuation after Week 8

For the management of subjects experiencing VF (and the resistance testing on samples from these subjects) see section 9.2.2.1 of the protocol.

Screening HIV-1 PR/RT genotype analysis will be performed for all subjects. Post-screening HIV-1 PR/RT genotype/phenotype testing will be available from subjects who are eligible for resistance testing (subjects with at protocol defined VF and have HIV-1 RNA ≥400 copies/mL). Note: baseline genotype/phenotype may be available for subjects with confirmed VF if they showed evidence of reduced susceptibility after VF to any of the study drugs.

